1.1 Specific Aims

This study aims to test methods of increasing adoption and integration of blood glucose monitoring into electronic medical records, and to measure the impact of widespread adoption on health status of patients with diabetes. To investigate determinants of adoption, the research will combine and test doctor and patient focused approaches to encouraging patient use of blood glucose flow sheets through the online patient portal, MyChart. Adoption will be measured on both the extensive and intensive margin: the number of patients who enter data into the flowsheets at all during the study period, and the mean number of entries per patient during the study period. Conditional on statistically significant increases in adoption, the study will examine corresponding intent-to-treat effects on patient health, and consider possible mechanisms through which health indicators improve or do not improve.

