2.3 Duration of Study

Primary care practices identified in the treatment group will be encouraged to place bulk orders for electronic glucose flowsheets over a period of two weeks. Patients will be actively encouraged to use flowsheets for 12 weeks following the administration period. Outcome data will be collected for a total of 38 weeks:

- (a) 12 weeks retrospective at baseline
- (b) 2 week administration period
- (c) 12 week implementation period
- (d) 12 week follow up period

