3.1.1 PRACTICE LEVEL PROMOTION

Providers in the randomly selected group of treatment primary care practices will be encouraged to batch order blood glucose flowsheets for all patients with diabetes with active MyChart accounts. The research team will contact physicians and practice managers with an explanation of the initiative and instructions for completing batch orders and viewing entries through the system. The practice will be advised to complete filling orders over a two week administration period, after which the implementation period will begin. A batch order will trigger two forms of alerts sent to providers, according to the default settings for electronic glucose flowsheets:

1. A bi-weekly report received of values that the patient has entered, or a notification that the patient has not entered data during the interval.
2. A notification when patient entered values are out of range (the patient also gets a notification that their doctor will see this value) according to the following current settings:

Notification Setting	Current Default
Pre-Meal Range (entry outside range=alert)	60-180 mg/dl
Post-Meal Range	100-240 mg/dl
Nighttime Range	60-300 mg/dl

Patients will automatically be notified when the flowsheet has been ordered for them. Additionally, providers will be given text for a secure smart-text message to send to all patients receiving the flowsheets, instructing them to enter data for the study period. The secure message will also provide them with information on how to enter data, and on the benefits of tracking blood glucose. Draft text of this message is included below:

Dear [Patient],

You may have seen that there is a new electronic form available for you to enter your blood glucose results in the MyChart portal. Keeping track of your blood glucose can help you manage your diabetes and reduce your chances for developing complications like heart disease, kidney damage and eye damage. As part of a new Inova program to help patients with diabetes get healthy, I would like you to try entering the results of your home blood glucose tests on MyChart for the next 3 months, through [Date]. Please let me know if you have any questions.

Sincerely,

[Practitioner]

WHAT TO DO NEXT

1. **Get help:** If you need help learning how to measure your blood glucose or getting testing supplies, you can contact [Practice Contact].

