3.4 Endpoints/Outcomes Measurements

Hypothesis: Interfacing with primary care practices to encourage physicians to implement default online orders of blood glucose flowsheets and informational messaging for all patients with diabetes will increase patient adoption.

Outcome Measures: Comparison of individuals between treatment and control practices-- (a) fraction of patients entering blood glucose measurements into MyChart flowsheets during implementation period & follow-up period (dichotomous), (b) mean number of flowsheet entries during implementation period and follow-up period (c) fraction of patients for whom order is placed by doctor

Hypothesis: Additional reminder messaging to patients that (1) emphasizes the value of tracking blood glucose data to the patient OR (2) emphasize the value of tracking blood glucose data to the doctor OR (3) informs patient of their selection for a chance to receive an award conditional on tracking will increase adoption relative to no reminder messaging.

Outcome Measure: Comparison of individuals across reminder messaging assignment groups (within treatment practices)-- (a) fraction of patients entering blood glucose measurements into MyChart flowsheets during implementation period & follow-up period (dichotomous), (b) mean number of flowsheet entries during implementation period and follow-up period

Hypothesis: Promotion of adoption of electronic blood glucose tracking through the means described above will result in the following intent-to-treat effects:

(a) reduction in patient A1c

Outcome Measures: Intent to treat comparison of individuals between treatment and control practices of the following measures at the end of the intervention period and follow-up period: (1) Mean A1c (2) Quartiles of A1c using quantile regression analysis (3) fraction of patients experiencing improvement [reduction] in A1c from baseline (dichotomous) (4) fraction of patients below benchmark 7.0% A1c (dichotomous)

(b) increase in frequency of doctor-patient interaction

Outcome Measures: Intent to treat comparison of individuals between treatment and control practices of the following measures during the intervention period and follow-up period: (1) number of securing messaging (2) number of phone interactions, and (3) number of in-office appointments

(c) changes to treatment plan path

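### The adjusted reminder-arm model leaves out flowsheet use before the first reminder, and Sections 1.1 and 3.4 do not clearly give one adoption window

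*Combined protocol and SAP*

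**What the plan says.** Section 1.1 defines the extensive margin of adoption as "the number of patients who enter data into the flowsheets at all during the study period", and hypothesis 1.2.1 refers back to that definition. Section 3.4 uses a narrower window, for the practice-level and reminder comparisons alike: the "fraction of patients entering blood glucose measurements into MyChart flowsheets during implementation period & follow-up period (dichotomous") and the "mean number of flowsheet entries during implementation period and follow-up period".

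Section 2.3 states "Outcome data will be collected for a total of 38 weeks" and lists the "2 week administration period" as a separate block between baseline and implementation. On what happens in that block, Section 3.1.1 says "The practice will be advised to complete filling orders over a two week administration period, after which the implementation period will begin", and adds: "Patients will automatically be notified when the flowsheet has been ordered for them". The same section describes a provider message to patients but gives no send date.

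Section 3.1.2 starts the research team's reminders after the administration period. Section 3.3 assigns them by the first letters of the last name and says that a causal reading requires last-name grouping to be unrelated to the likelihood of adoption. The adjusted model in Section 4.2 contains age and gender, race/ethnicity, baseline A1c, days since the last office visit, doctor fixed effects and a flag for an overlapping study. It contains no earlier flowsheet use.

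**The concern.** For the reminder comparison, entries made after the order but before the first reminder cannot have been caused by any reminder. Earlier use of the same feature is plausibly among the better predictors of later use. Leaving it out gives up precision in a comparison for which Section 3.1.2 already allows arms to be dropped to preserve power. It also gives up a check that this design needs more than most. Assignment is not random, and the only safeguard named in Section 3.3 is adjustment for recorded race/ethnicity. Pre-reminder use is the most direct evidence available on whether the last-name groups already differ in their readiness to adopt.

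For the practice-level comparison, the question is which weeks count. The weeks omitted from Section 3.4 are those in which the feature is switched on in treatment practices and the automatic notice goes out. Control practices receive no encouragement, so entries left out would come almost entirely from the treatment side. Section 1.1 makes the health analysis depend on a significant rise in adoption, so the definition of that outcome should not be open to two readings.

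**Working it through.** **Inputs (Section 4.1).** Reminder comparison: 3,600 patients, 4 arms (900 each if equal), 20% adoption without reminders. Practice comparison: 7,200 patients, 24 practices (12 per arm, mean size 300), 2% control adoption, intra-cluster correlation 0.1. Alpha and power are not stated; I assume two-sided 0.05 and 80%.

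**Step 1: reproduce the reminder figure.** The minimum detectable effect (MDE) d solves

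d = 1.96·√[2p̄(1−p̄)/n] + 0.8416·√{[p0(1−p0) + p1(1−p1)]/n}

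with n = 900, p0 = 0.20, p1 = 0.20 + d and p̄ their mean. The solution is d = 5.53 points, which agrees with the stated 5.5.

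**Step 2: add pre-reminder use.** If it correlates ρ with the outcome, residual variance falls by the factor 1 − ρ², equivalent to n = 900/(1 − ρ²) per arm. The documents give no value of ρ, so a range is shown.

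| ρ (assumed) | equivalent n per arm | MDE, points |
|---|---|---|
| 0 | 900 | 5.5 |
| 0.1 | 909 | 5.5 |
| 0.3 | 989 | 5.3 |
| 0.5 | 1,200 | 4.8 |
| 0.6 | 1,406 | 4.4 |

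**Step 3: compare the windows.** Section 2.3 gives 12 + 2 + 12 + 12 = 38 weeks. Section 3.4 counts 12 + 12 = 24 of the 26 weeks from the start of administration. In the dichotomous outcome, a patient is lost only by entering data in the first two weeks and never in the following 24. The entry count loses every entry made in those two weeks.

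**Step 4: reproduce the practice-level figure.** Design effect = 1 + 299 × 0.1 = 30.9, so effective n per arm = 3,600/30.9 = 116.5. For 11.5% against 2%, SE = √[(0.02 × 0.98 + 0.115 × 0.885)/116.5] = 0.0323 and 0.095/0.0323 = 2.94. Noncentral t on 22 df gives power of 80%, which agrees with the stated 9.5 points.

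**Step 5: what the window could cost.** Suppose a share of treated adopters enter only in the first two weeks, and none do so in control practices. The shares are assumed; the documents give none. The treated rate in the Section 3.4 window is then the true rate × (1 − share).

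| share lost | true rate 11.5%: difference, power | true rate 20%: difference, power |
|---|---|---|
| 0 | 9.5 points, 80% | 18.0 points, 99.2% |
| 5% | 8.9 points, 77% | 17.0 points, 98.8% |
| 10% | 8.35 points, 73% | 16.0 points, 98.1% |
| 20% | 7.2 points, 64% | 14.0 points, 95.7% |

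The 20% column takes Section 4.1's no-reminder rate, which is applied there to all 3,600 treatment-practice patients, as the treated rate.

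**The case against.** A reader might infer that the practice-level effect is understated against the protocol's own definition and that the study loses power as a result. The documents do not support that.

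- The study period in Section 1.1 carries no dates. Sections 3.1.1 and 6.2 use the same term for roughly the three-month tracking window, so Section 3.4 can fairly be read as giving a loose phrase its operational meaning.
- The effect in the Section 3.4 window is a different estimand, not a biased one.
- Patients who carry on are counted, and three of the four groups are reminded every two weeks. Nothing in the documents says what share would stop after the roll-out.
- The power losses in the 11.5% column treat the MDE as the true effect, where power is 80% by construction and any loss shows.
- A common start at implementation is defensible, because access is staggered during roll-out. For the reminder comparison it is the correct start.

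All of this stands. It is also fair to say that the gain from the covariate depends on an unknown correlation and is negligible at 0.1. A patient whose order came late in the two weeks has had little chance to enter anything, so zero use partly reflects order date. That is a reason to include order date, not to leave out the covariate. The objection does not remove the need for a dated window, and it does not touch the value of a balance check under last-name assignment.

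**Conclusion.** No stated figure is wrong and no planned analysis is invalid. The main point is an inexpensive improvement: the adjusted reminder model should use flowsheet activity before the first reminder. The gain in MDE runs from nothing visible (5.5 points at a correlation of 0.1) to about 1.1 points (4.4 at 0.6), assuming equal arms of 900, two-sided 0.05 and 80% power. The balance check is useful whatever the correlation.

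The secondary point is one of definition. Sections 1.1 and 3.4 do not clearly give the same adoption window, and Section 3.4 omits the weeks of ordering and automatic notification. How much this matters cannot be set from the documents. At the protocol's own 20% rate, power stays between 96% and 99% across the losses tried.

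**What to change.** **Reminder comparison.** Keep the implementation and follow-up window for the outcome. In the adjusted model of Section 4.2, add any entry before the first reminder, number of entries before the first reminder, and order date. Report the balance of these across the last-name groups, as a check on the assumption in Section 3.3.

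**Practice-level comparison.** Put dates to the study period and state one adoption window in both Sections 1.1 and 3.4. Alternatively, keep the Section 3.4 window and report beside it the count from the start of administration to the end of follow-up, in both arms. Do not adjust this comparison for early entries: they arise after the practices are randomised and are part of the effect.

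**Cost.** The outcome data already span the administration period, so this needs query dates, three added covariates, a balance table and a sentence or two of text, fixed before the outcome data are analysed. No new data collection is needed.

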1.2 Hypotheses

1.2.1 Interfacing with primary care practices to encourage physicians to implement default online orders of blood glucose flowsheets and informational messaging for all patients with diabetes will increase patient adoption (as defined above).

1.2.2. Additional reminder messaging to patients that (1) emphasizes the value of tracking blood glucose data to the patient OR (2) emphasize the value of tracking blood glucose data to the doctor OR (3) informs patient of their selection for a chance to receive an award conditional on tracking will increase adoption relative to no reminder messaging.

1.2.3 Promotion of adoption of electronic blood glucose tracking through the means described above will result in the following intent-to-treat effects:

- (a) reduction in patient A1c
- (b) increases in frequency of doctor-patient interaction
- (c) changes to treatment plan path

1.2.4 Reminder messaging treatments that induce more intensive use of flowsheets will lead patients to experience larger effects as described in 1.2.3.

1.2.5 Entries of blood glucose data will be predictive of A1c on average and will lower over the study period.

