4.1 Sample Size

Non-pregnant adult patients of Inova primary care physicians with a current diabetes mellitus diagnosis and active MyChart account at time of treatment administration will be included in the study. The estimated number of patients is around 7200, from 71 primary care physicians across 24 selected Inova primary care practices.

Power Calculations

Power calculations were performed using the “clustersampsi” command in Stata. Knowledge of available sample and estimates/assumptions of control outcome mean, variance, and intraclass correlation were used to calculate a minimum detectable effect size for the key outcomes of flowsheet adoption (extensive margin, dichotomous rate of adoption) and changes in mean A1c.

Flowsheet Adoption: Practice Level Treatment-Control Comparison

Sample Size: 7200

Number of Treatment Arms: 2

Number of Clusters: 24

Assumed Control Adoption Rate: 2%

Assumed Intra-Cluster Correlation (within practices): 0.1

Minimum Detectable Effect: **9.5 percentage point increase in flowsheet orders**

Mean HbA1c: Practice Level Treatment Control Comparison

Sample Size: 7200

Number of Treatment Arms: 2

Number of Clusters: 24

Assumed Control HbA1c Mean: 6.74

Assumed Control HbA1c Standard Deviation: 1.39

Assumed Intra-Cluster Correlation (within practices): 0.07

Assumed Baseline Correlation: 0.80

ITT Minimum Detectable Effect: **0.27 change in A1c**

Flowsheet Adoption: Individual Level Comparison between Messaging Assignment Groups in Treatment Practices

Sample Size: 3600

Number of Arms (including no reminder): 4

Assumed No Reminder Adoption Rate: 20%

Minimum Detectable Effect: **5.5 percentage point increase in use of flowsheets when compared to no reminder**

Justification

The sample size represents the entire population of Inova primary care patients with diabetes who have active MyChart accounts and are therefore able to access the blood glucose tracking feature. The minimum detectable effects resulting from power calculations above are in-line with similar studies cited in the protocol background. Metastudy reviews of the effect of self monitoring of blood glucose found a 0.33 point change in A1c.

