4.2 Method of Data Analysis

All data analyzed in this study will be administrative health and use data that is collected as part of routine medical care and record keeping. EPIC has offered to build the SQL queries required to produce the outcome datasets described in this protocol. Outcomes listed in Section 3.4. will be analyzed using regression analysis, including (a) a version with no covariates, (b) a version controlling for patient age/gender, race/ethnicity, A1c at baseline, days since most recent office visit at baseline, and doctor fixed effects. A flag identifying patients who are eventual participants of "Impact of Innovative Interventions on Diabetic Adherence with Digital Sensors" (a study recently submitted to the IRB that may have limited overlap with this population) will also be included in the controls. For outcomes indicating analysis of practice level treatment and control groups, standard errors will be clustered at the practice level.

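### Once adoption has risen, the A1c-reduction hypothesis rests on 12 contrasts with no deciding test, so a programme that leaves A1c unchanged shows a significant reduction in about one trial in ten

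*Combined protocol and SAP*

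**What the plan says.** Section 1.2.3 states the health hypothesis as a single directional claim: "a) reduction in patient A1c". Section 3.4 attaches four measures to it: "1) Mean A1c (2) Quartiles of A1c using quantile regression analysis (3) fraction of patients experiencing improvement [reduction] in A1c from baseline" and "4) fraction of patients below benchmark 7.0% A1c (dichotomous". They are to be compared between treatment and control practices "at the end of the intervention period and follow-up period".

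Three other places bear on how the claim would be decided:

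- Section 1.1 sets an order: "Conditional on statistically significant increases in adoption, the study will examine corresponding intent-to-treat effects on patient health".
- Section 4.1 computes minimum detectable effects for the "key outcomes of flowsheet adoption (extensive margin, dichotomous rate of adoption) and changes in mean A1c". Mean A1c is the only A1c measure given a power calculation.
- Section 4.2 runs each outcome in two specifications, "a) a version with no covariates, (b) a version controlling for patient age/gender" and further covariates including baseline A1c.

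The available text names no deciding A1c measure or time point, states no significance level, and gives no multiplicity rule for the A1c measures.

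**The concern.** One claim has many ways to succeed. A flat mean with a significant lower quartile at one time point could be reported as support for the hypothesis. The same data could equally be reported as failing to support it, because the mean did not move. The plan does not say which reading is correct.

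Adoption without an A1c benefit is a realistic outcome here: section 1.3 cites a randomized trial in which self-monitoring without additional training had no effect on A1c at one year. A1c is also the trial's measure of patient health, and section 11 says a collaborating agency will carry the results into guidelines and informational materials. An isolated chance finding could therefore travel some distance.

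**Working it through.** **Inputs from section 4.1.** 7,200 patients, 24 practices, control mean A1c 6.74, SD 1.39, ICC 0.07, baseline correlation 0.80, stated minimum detectable effect (MDE) 0.27. For adoption: ICC 0.1, 2% in control practices, 20% in treatment practices without reminders.

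**Assumed, because not stated.** Two-sided 5% and 80% power; 12 practices per arm of 7,200/24 = 300 patients each; A1c available for every patient; the correlation between the two outcome times.

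**1. Reproduce the plan's figure.**
- Design effect = 1 + 299 × 0.07 = 21.93.
- SE without baseline = 1.39 × √(2/3600 × 21.93) = 0.1534.
- SE with baseline = 0.1534 × √(1 − 0.80²) = 0.1534 × 0.6 = 0.0921.
- MDE = (2.074 + 0.858) × 0.0921 = 0.270, using t quantiles on 22 df. This matches the stated 0.27.
- One-sided 5% would give 0.237 and 90% power 0.313, so two-sided 5% with 80% power is a sound inference.
- Without the baseline adjustment the same formula gives 0.27/0.6 = 0.45.

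**2. Count the contrasts.** Mean (1) + quartiles (3) + fraction improved (1) + fraction below 7.0% (1) = 6 per time point, and 6 × 2 = 12. Two model specifications make up to 24 p-values.

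**3. Upper bound.** If the 12 tests were independent, 1 − 0.95¹² = 46%. They are strongly correlated, so simulation is needed.

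**4. Null simulation of A1c.** There were seven scenarios with 2,000 trials each, using the inputs above and values rounded to 0.1. Tests were practice-level t tests on 22 df at two-sided 5%. Quartiles were tested through the proportion of patients below the pooled quartile. Scenarios varied the correlation between outcome times (0.6 to 0.9), the practice-level correlation over time (0.5 to 0.95) and skewness. Monte Carlo error near 20% is √(0.2 × 0.8/2000), about 0.9 points.

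| What counts as a positive A1c result | Null rate |
|---|---|
| Any of 12, either direction, no covariates | 17–22% |
| Any of 12, either direction, adjusted for baseline A1c | 14–20% |
| Any of 24 (either specification counts), either direction | 23–27% |
| Any of 12 towards reduction, one specification | 7–11% |
| Any of 24 towards reduction | 11–14% |
| Mean A1c only, two time points, either direction | 6–10% |
| Mean A1c, one time point, one specification | 4.3–5.2% |

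A single two-sided 5% test gives a false reduction 2.5% of the time.

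**5. Effect of the adoption condition in section 1.1.** If the programme changes nothing, adoption must first rise significantly by chance.
- That has probability 2.5% for one adoption measure.
- It is at most about 1 − 0.975⁵ = 12% for any of five independent ones (entry yes/no and number of entries in each of two periods, plus orders).
- The chance of then seeing any significant A1c result is roughly 0.025 × 0.17 = 0.4% to 0.12 × 0.27 = 3%, taking adoption and A1c as independent under the null.

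Under the plan's own adoption figures the condition is nearly always met:
- Effective sample per arm = 3600/(1 + 299 × 0.1) = 116.5.
- SE = √[(0.02 × 0.98 + 0.20 × 0.80)/116.5] = 0.0393.
- 0.18/0.0393 = 4.58, against a critical value of 2.074: power about 99%.

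**The case against.** The strongest defence is that the plan has more structure than a bare list of endpoints.

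- **The adoption condition is a real hierarchy.** A reader might infer that a programme with no effect at all would show a significant A1c result one time in five. The documents do not support that: such a programme rarely reaches the A1c tests, and step 5 puts its rate at no more than about 3%. This stands. But the condition gives no protection once adoption rises, which is what the plan expects.
- **Mean A1c is already singled out.** A reader might also infer that the plan gives no indication of a leading measure. Section 4.1 does give one. If it is taken as a designation, only the time point and specification stay open, and the time point alone gives 6% to 10% two-sided. But the wording introduces a power calculation and does not rank the other measures below the mean.
- **The hypothesis is directional.** A significant rise in A1c cannot support it, so the figure relevant to the claim is about one in ten, not one in five. This stands.
- **The count of 12 is a reading.** Quartile regression may be meant as one description of the distribution, and nowhere does the plan say that any single significant result confirms the hypothesis. Nor does it say what would, and that is the gap.
- **The simulation is a simplification.** It uses practice-level t tests in place of the planned regressions, equal practices and complete A1c, and its covariate model adjusts for baseline A1c only. The rates are therefore approximate, although they were similar across the scenarios tried.

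**Conclusion.** The concern holds for a programme that raises adoption but leaves A1c unchanged. In that case at least one of the 12 contrasts is significant in about one trial in five, and in about one in ten towards reduction, roughly three to four times the 2.5% of a single test (7/2.5 = 2.8 to 11/2.5 = 4.4). On the most generous reading, where mean A1c alone decides, the excess shrinks to 6–10% against 5% two-sided. Which of these applies depends on a rule the plan does not contain.

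The figures rest on two-sided 5% testing, 12 against 12 equal practices, A1c available for all patients and an assumed correlation between the two outcome times. The absence of a deciding test rests on none of these. This should be corrected before outcome data are seen.

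**What to change.** Add to section 3.4 that, after the adoption condition in section 1.1 is met, hypothesis 1.2.3(a) is decided by one test: the treatment-control difference in mean A1c, adjusted for baseline A1c, with practice-clustered errors, at one time point named before data are seen. Label the following as secondary, reported with estimates and confidence intervals: mean A1c at the other time point, the quartiles, the fraction improved and the fraction below 7.0%. If a secondary result is to support a claim, apply Holm within that set, and only when the deciding test is significant.

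Two details need care:

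- **Specification.** The deciding model must include baseline A1c, because the 0.27 MDE depends on it (0.45 without). Write the model out in full: specification (b) also lists doctor fixed effects, which would absorb a practice-level treatment term if each doctor works at one practice. That is a separate matter.
- **Time point.** The choice is the sponsor's. End of follow-up, for example, falls 12 + 12 = 24 weeks after implementation starts and so matches by calendar the 24-week and six-month evidence in section 1.3, but active encouragement ends at week 12.

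The cost is a few sentences, with no new data and no loss of power for the one A1c measure that section 4.1 powers. Bonferroni over all 12 would also control the error, but at a simulated 1.3–2.4% it is needlessly strict. The downside is that an isolated quartile or threshold result can no longer confirm the hypothesis.
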